#### 7.4.4 Missing Data

The CGM measures interstitial glucose every 5 minutes, but glucose data may be missing due to signal disruption or mechanical dislodgment. Periods of missing data for more than

20 minutes will not be replaced. For data gaps of up to 20 minutes, the two glucose values preceding and following the missing period will be averaged and used to replace the missing data.

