### 7.4 Statistical Methods

#### 7.4.1 Analysis of Primary and Secondary Outcomes of Interest

Primary objective: Determine the feasibility of at-home, CGM-based glycemia evaluation as measured by adequacy of CGM data capture and nutrition logging quality and completion on days of at-home glucose and mixed-meal challenge.

*H1a: Complete CGM data will be available for  $\geq 80\%$  of requested days worn:* The number of days with adequate CGM data will be divided by 9, omitting the first 24 hours due to possible inconsistent measurements after initial placement. Feasibility will be defined as  $\geq 80\%$  (7.2) of days with data.

*H1b: Documentation of glucose and mixed-meal challenge will be complete and adequate for analysis for  $\geq 80\%$  of participants:* The number of participants who document the date and time of glucose and mixed-meal ingestion (including mixed-meal content) will be determined and divided by the total number of participants. Feasibility will be defined as  $\geq 80\%$  of participants documenting date and time of either the glucose challenge, mixed-meal challenge, or both.

Secondary objective: Determine the test performance characteristics of at-home, CGM-measured glucose challenge with laboratory-based 2-hour OGTT.

*H2: CGM-measured glucose 2 hours and 5 minutes after standardized glucose ingestion will have adequate discrimination of normal ( $<140$  mg/dL) versus dysglycemic ( $\geq 140$  mg/dL) 2-hour OGTT glucose, as assessed by area under the receiver operating characteristic curve  $\geq 0.7$ :* Using participant logs via text message survey or paper-based logs, date and time of home glucose challenge will be determined and labeled in CGM data. A time point 2 hours and 5

---

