minutes later (accounting for lag due to interstitial measurement)(Wadwa, Laffel et al. 2018) (CGM-2h) will serve as the comparison to the 2-hour glucose during OGTT obtained at the study visit (OGTT-2h). Sensitivity, specificity, and positive and negative predictive values of CGM-2h to predict OGTT-2h $\geq$ 140 mg/dL will be assessed for various thresholds of CGM-2h. Area under the receiver operating characteristic curve (AUC) will be determined. An AUC threshold of  $\geq$ 0.7 will be used to define adequate discrimination. The same analysis will be repeated for the comparison of baseline CGM glucose (at time of glucose ingestion) to fasting glucose on OGTT, using a fasting glucose threshold of  $\geq$ 100 mg/dL to define dysglycemia. Finally, correlation analyses (Spearman or Pearson depending on distribution) will be performed to further explore the relationship between CGM indices obtained during at-home glucose challenge (e.g., baseline, peak, mean glucose) and both laboratory-measured HbA1c and plasma glucose during OGTT. Correlations will be examined across subgroups such as lower versus higher ActiGraph-measured physical activity level and self-reported carbohydrate intake on the day prior to at-home glucose challenge, age, pubertal stage, and body mass index.

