#### 7.4.3 Exploratory analyses

The analyses for at-home glucose challenge described above will be repeated to evaluate the test performance of at-home mixed-meal challenge in comparison to 2-hour OGTT. In addition, CGM metrics such as average, area under the curve, and peak glucose as well as coefficient of variation will be compared for days of CGM wear without glucose or mixed-meal challenge versus challenge days to assess the difference in glucose trends of typical daily life versus those artificially imposed by testing.

An additional exploratory analysis will use responses from the disordered eating questionnaire to assess whether correlations between OGTT and CGM-measured glycemia differ between youth with higher versus lower self-report of loss-of-control eating.

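### Filling CGM gaps of up to 20 minutes with one constant average adds avoidable error to an off-centre CGM-2h; time-based linear interpolation would remove nearly all of it (minor point)

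*Combined protocol and SAP*

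**What the plan says.** Section 7.4.4 gives the sampling rate ("The CGM measures interstitial glucose every 5 minutes"), leaves gaps longer than 20 minutes unfilled, and sets the rule for shorter ones: "the two glucose values preceding and following the missing period will be averaged and used to replace the missing data". There is no time weighting, no exception for key time points, and no sensitivity analysis. The wording does not settle whether one reading or two on each side of the gap enter the average. Either way the result is one constant for the whole gap.

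The filled series feeds these analyses:

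- **H2 (Section 7.4.1)** uses one value per participant, "CGM-measured glucose 2 hours and 5 minutes after standardized glucose ingestion", called CGM-2h. The extra 5 minutes allows for interstitial lag. The plan then reports "Sensitivity, specificity, and positive and negative predictive values of CGM-2h to predict" a 2-hour OGTT glucose of at least 140 mg/dL, with an ROC area of at least 0.7 as the criterion.
- **Baseline (Section 7.4.1)** repeats this for "baseline CGM glucose (at time of glucose ingestion) to fasting glucose on OGTT".
- **Correlations (Section 7.4.1)** use "CGM indices obtained during at-home glucose challenge (e.g., baseline, peak, mean glucose").
- **Exploratory work (Section 7.4.3)** repeats the H2 analysis for the mixed meal and compares "CGM metrics such as average, area under the curve, and peak glucose as well as coefficient of variation" between challenge and non-challenge days.

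**The concern.** Two hours after a glucose load the curve is usually still moving. A constant equal to the average of the bounding readings represents the middle of the gap, not the moment of each missing reading. If the 2 h 05 min point lies off-centre in a gap, the value recorded as CGM-2h belongs to a different time. The plan moves its index time by 5 minutes for sensor lag, so it treats a shift of that size as worth correcting. The filling rule can introduce a shift as large, or larger, in either direction. H2 uses a single reading per participant, so averaging over other readings does not dilute the error.

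**Working it through.** The plan states no figure to reproduce here. The check is direct arithmetic.

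**Inputs.** From Section 7.4.4: 5-minute spacing, a 20-minute limit and the averaging rule. From Section 7.4.1: CGM-2h is read at 125 minutes. Assumed, because the documents give no value: slopes of 0.5, 1 and 2 mg/dL/min.

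**Readings per filled gap.** If the 20 minutes counts missing readings, at most 20/5 = 4 are filled. If it is the interval between the bounding readings, at most 20/5 − 1 = 3 are.

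**Formulas.** Let k readings be missing between bounding values A and B, with j = 1, …, k.

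- Flat fill: (A + B)/2 for every j.
- Linear fill: A + (B − A) × j/(k + 1).
- Distance of reading j from the gap midpoint: 5 × (j − (k + 1)/2) minutes.
- On a straight segment of slope s, the flat-fill error is −s × 5 × (j − (k + 1)/2) and the linear-fill error is 0.

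**Largest error of the flat fill on a straight segment**

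| Missing readings | Time shift (min) | 0.5 mg/dL/min | 1 mg/dL/min | 2 mg/dL/min |
|---|---|---|---|---|
| 1 | 0 | 0 | 0 | 0 |
| 2 | 2.5 | 1.25 | 2.5 | 5 |
| 3 | 5 | 2.5 | 5 | 10 |
| 4 | 7.5 | 3.75 | 7.5 | 15 |

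The last three columns are in mg/dL. The time-shift column needs no assumed slope. Averaging two readings on each side gives the same errors on a straight segment.

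**Sign.** With four missing on a fall of 1 mg/dL/min, the errors in order are −7.5, −2.5, +2.5 and +7.5, which sum to zero. On a rise the signs reverse.

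**Example.** Take a true CGM-2h of 143 mg/dL, falling at 1 mg/dL/min.

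- First of four missing: the bounds are 148 and 123. Flat fill is (148 + 123)/2 = 135.5; linear fill is 148 − 25 × 1/5 = 143.
- Last of four missing: the bounds are 163 and 138. Flat fill is 150.5; linear fill is 163 − 25 × 4/5 = 143.

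**Curved profile.** Assume glucose = 95 + 85 × (t/45) × exp(1 − t/45), which peaks at 180 mg/dL at 45 minutes. If the 125-minute reading is the last of four missing, its true value is 134.9; the flat fill is 4.8 mg/dL too high and the linear fill about 0.3. If it is the last of three, the errors are about 3.2 and 0.2.

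**Summary measures**, with one bounding value per side:

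- *Gap mean.* The linear values sum to k(A + B)/2, the same as the flat values.
- *Trapezoidal glucose area.* Both fills give 5(k + 1)(A + B)/2.
- *Peak.* Neither fill can exceed the larger bounding reading, which is already in the record, so the recorded peak is the same.
- *SD.* On a straight fall of 1 mg/dL/min with four missing, the SD over the 25-minute window drops from 9.35 to 7.91 with the flat fill and stays at 9.35 with the linear fill. That is one short window, so the effect on a whole-day CV is slight.

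**The case against.** The strongest case against is that this hardly matters. An error needs two or more consecutive missing readings, a gap that covers one particular 5-minute point, that point off-centre, and a curve that is moving. If 1% to 3% of the 32 expected evaluable participants met those conditions (an assumption), that would be 0.3 to 1.0 participants. With an assumed 16/16 split on the OGTT, one participant moving past two of the other group changes the ROC area by 2/256, about 0.008. Ingestion time is also self-reported at the next survey. At 1 mg/dL/min, an assumed 5-minute reporting error moves CGM-2h by 5 mg/dL, and it can occur in anyone. All of this stands and limits the weight of the point. None of it favours the flat fill.

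A reader might also infer more than the documents support:

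- *That CGM-2h is biased in one direction.* Errors within a gap are equal and opposite on a straight segment, and nothing suggests that gaps fall to one side of 2 h 05 min. Across participants the rule adds noise.
- *That peak, mean or glucose area is distorted.* The working shows they match linear interpolation. If the true peak lies inside the gap, neither method recovers it.
- *That participants are misclassified at a CGM cut-off of 140 mg/dL.* That value defines the OGTT reference. CGM-2h is examined at several thresholds, and H2 is judged on ROC area, which depends on ranks.
- *That baseline is equally exposed.* It follows a fast of at least 10 hours, when the curve should be nearly flat, so the difference is small unless the gap runs well into the rise.

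**Conclusion.** The point holds as a minor, free improvement. The flat fill shifts the effective time of an off-centre CGM-2h by up to 2.5, 5 or 7.5 minutes for two, three or four missing readings; the last applies only if the 20 minutes counts missing readings. In glucose terms this is up to 2.5, 5 or 7.5 mg/dL at 1 mg/dL/min, and half or double that at 0.5 or 2. These slopes are assumptions, and the gap frequency is unknown. A single missing reading, or the exact middle reading of a gap, is unaffected on a straight segment.

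The consequence is avoidable measurement error in the H2 index test, and in its mixed-meal counterpart, for the probably few participants with such a gap. It would be wrong to read this as a threat to the feasibility result. H1a counts days with adequate data and H1b counts documented challenges, and both fills complete the same readings.

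**What to change.** Replace the last sentence of Section 7.4.4 with: 'Gaps of up to 20 minutes will be filled by linear interpolation in time between the last reading before and the first reading after the gap.'

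This is exact on a straight segment and leaves only a small curvature error near 2 hours. It also settles how many readings on each side are used. It would help to add whether the 20 minutes counts missing readings or the interval between the bounding readings.

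A sensitivity analysis omitting participants whose CGM-2h was interpolated is optional. It would probably drop very few people, but reporting how many CGM-2h values were filled would show whether the issue arose at all.

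The cost is one sentence of analysis wording. No new data are needed and nothing is lost.

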### **7.5 Sample Size and Power**

The sample size for this pilot study balances feasibility with the likelihood of obtaining meaningful results for future studies. Assuming 20% drop-out or incomplete data, a sample size of 40 should lead to 32 evaluable subjects. This will allow for subgroup analyses, including by sex and physical activity strata (high versus low). This study will include nearly twice as many participants with known dysglycemia (or more if previously undiagnosed) as those without in order to maximize the ability to compare impaired glucose tolerance and abnormal CGM-measured glucose trends.

## 8 SAFETY MANAGEMENT

### 8.1 Clinical Adverse Events

Clinical adverse events (AEs) will be monitored throughout the study.

### 8.2 Adverse Event Reporting

Since the study procedures are not greater than minimal risk, serious adverse events (SAEs) are not expected. If any unanticipated problems related to the research involving risks to subjects or others happen during the course of this study (including SAEs) they will be reported to the IRB in accordance with institutional guidelines. AEs that are not serious but that are notable and could involve risks to subjects will be summarized in narrative or other format and submitted to the IRB at the time of continuing review.

The relationship of each SAE to the study intervention will be characterized using one of the following terms in accordance with IRB Guidelines: definitely, probably, possibly, unlikely or unrelated.

### 8.3 IRB/IEC Notification of SAEs and Other Unanticipated Problems

The Investigator will promptly notify the IRB of all on-site unanticipated, serious Adverse Events that are related to the research activity. Other unanticipated problems related to the research involving risk to subjects or others will also be reported promptly. Written reports will be filed using the electronic IRB system and in accordance with the timeline below. External SAEs that are both unexpected and related to the study intervention will be reported promptly after the investigator receives the report.

Type of Unanticipated Problem	Initial Notification (Phone, Email, Fax)	Written Report
Internal (on-site) SAEs Death or Life Threatening	24 hours	Within 2 calendar days
Internal (on-site) SAEs All other SAEs	7 days	Within 7 business days
Unanticipated Problems Related to Research	7 days	Within 7 business days
All other AEs	N/A	Brief Summary of important AEs may be reported at time of continuing review

#### 8.3.1 Follow-up report

If an SAE has not resolved at the time of the initial report and new information arises that changes the investigator's assessment of the event, a follow-up report including all relevant new or reassessed information (e.g., concomitant medication, medical history) will be submitted to the IRB. The investigator will be responsible for ensuring that all SAE are followed until either resolved or stable.

### 8.4 Investigator Reporting of a Serious Adverse Event to Sponsor

Reporting will be consistent with National Institutes of Health requirements.

### **8.5 Medical Emergencies**

Medical emergencies that might develop during the course of the study at PCTR will be referred to the CHP emergency room. Medical emergencies that might develop during the course of the study during the at-home intervention will be referred to local emergency medical services.

## 9 STUDY ADMINISTRATION

### 9.1 Data Collection and Management

The PI is responsible for the accuracy and completeness of data collection and management. The PI may designate qualified individual(s) to collect data and manage data. Only investigators and research staff that have completed appropriate IRB training and approval and are listed on the IRB approved protocol are eligible to collect and work on information from the study. Future studies that may use patients or data collected from this study must have separate approved IRB protocols and consent forms, if applicable.

REDCap Case Report Forms (CRF): REDCap CRFs will be created by the study team for data capture. REDCap is a secure web-based data management software designed by Vanderbilt University investigators. Study data will be entered through intelligent REDCap forms that adapt to data content, and include built-in error checks to trap out-of-range or inconsistent entries into the central database. Original data will be recorded directly into CRFs by the study coordinator or a study investigator after consent is documented. Copies of laboratory, physical exam, anthropometric, and questionnaire responses will be received through the electronic medical record or through secured email. This information also will be recorded into CRFs in REDCap. The password to log into REDCap will be unique to each member of the study team. REDCap will also be used to collect disordered eating questionnaire responses.

Dexcom G6 Pro Data: Dexcom Clarity for Health (<https://clarity.dexcom.com/professional/>) will be used to upload CGM data. Only study IDs will be used, without identifiable patient information. A separate “clinic” will be created for this research project on the website, with a separate login created for each study team member. The PI and primary research coordinator will have Administrator privileges for data access and uploads; additional study staff will be added for view or upload only, without editing privileges.

ActiGraph GT9X Link Data: ActiLife 6 software will be used to upload and analyze anonymized actigraphy data. This software will be on the PI’s UPMC desktop computer, and uploaded data will be saved to the PI’s UPMC secure shared drive.

Text Message-Based Survey Data: Following enrollment, study staff will obtain the phone number for the participant or participant parent’s text message-enabled cellphone in order to send and receive text message based nutrition, activity, and sleep surveys. No PHI will be shared with the text message platform Mosio.

Interview Data: Written data collected during the interview will be stored in a secure file cabinet in the PI’s office. Only the research team will have access to interview notes, which will be destroyed after a minimum of 7 years after completion of the study. Interviews will also be audio-recorded. Audio recordings will be kept as digital files and kept on the PI’s password-protected institutional shared drive. Recordings will be destroyed after the recordings are transcribed and qualitative analysis is complete.

---

Participant Recruitment Log: This password-protected Microsoft Excel file, saved on the PI's institutional shared drive will include patient identifying information necessary for registration, enrollment, and follow-up. Following enrollment, this document will be used to maintain a log of enrolled patients. For patients who are not enrolled, patient-identifying information will be destroyed. A non-identifiable list of patients that were not enrolled will be retained for the purpose of calculating response rate.

Consent Forms: Electronic copies of the consent forms will be stored in a password-protected folder on the PI's shared drive. Participants will be emailed their signed consent form. If a participant turns 18 during the study, consent will be re-obtained electronically via REDCap.

Anonymization: Data will be extracted from REDCap, Dexcom Clarity, and ActiLife software and downloaded onto the PI's secure UPMC shared drive. Datasets will be stripped of all identifiers and individuals will be referred to by their study ID. The study ID will also be used on all analytical files.

## **9.2 Confidentiality**

All data and records generated during this study will be kept confidential in accordance with institutional policies and on HIPPA subject privacy. The investigators/study team members/site personnel will not use such data and records for any purpose other than for conducting the study.

As a way to minimize the chance of PHI (protected health information) from being disclosed, a unique identification code will be used for each participant. Specific keys will be saved in an encrypted format on the PI's secure institutional shared drive.

Participants will not be identified by name/PHI on any publications that result from this research.

The information collected as part of this study will be kept for 7 years after study completion. At that time, the information collected will be destroyed or all identifiable information will be removed. All keys will be destroyed at this time, as well. No identifiable data will be used for future studies without first obtaining IRB approval.

## **9.3 Regulatory and Ethical Considerations**

### **9.3.1 Data and Safety Monitoring Plan**

Due to the minimal risk involved in the investigation, a Data and Safety Monitoring Board (DSMB) is not applicable. Study data will be carefully monitored by the PI. The PI will provide weekly supervision to a trained clinical research coordinator who will be involved in data collection. The study team will monitor and track collection of all study data. The team will additionally track all protocol deviations and adverse events and will report these to the IRB, in accordance with reporting guidelines.

---

### 9.3.2 Risk Assessment

Study participation poses no more than minimal risk. Expected risks by procedure are as follows:

**Phlebotomy and IV insertion:** The blood volume collected will be approximately 18 mL. The blood volume removal is much less than the maximum blood volume removal per 8-week period recommended by OHRP (children < 7 mL/kg over 6 weeks). IV insertion and phlebotomy will be done by trained PCTRc nurses. There is a risk of bruising and discomfort at the venipuncture site. Blood draw may result in temporary discomfort from needle stick, bruising, fainting, weakness, and rarely an infection at the site. To minimize discomfort, a topical numbing cream or spray will be offered. Slight swelling of the skin in response to the numbing medicine may occur in approximately half of all individuals. This goes away within about 4 hours in most cases.

**Overnight Fast:** Fasting may cause hunger pangs, upset stomach, headache, or light-headedness. However, the requested fasting period is no longer than usual for most individuals, and none of the participants will be taking medications that would place them at risk for hypoglycemia.

**Anthropometric measurements and pubertal status:** Exam poses minimal risks. The anthropometric assessment involves measurements of height, weight, and circumferences. Some individuals are uncomfortable with physical examinations. For this reason, during the encounter each step will be explained to the participant explicitly. Drapes and other barriers will be used if they are required to disrobe during the exam. The exam will be performed by staff experienced in obtaining measurements in children at all levels of cognitive ability. The measurements are obtained in a private room. The parent is permitted to stay with the child if it increases their comfort with the exam.

The puberty assessment will be performed by a pediatric endocrinologist in a private setting. The procedure will be explained to the child in advance, and the parent is permitted to be present if preferred by the child. The exam is performed by highly experienced personnel who are familiar with minimizing distress associated with the exam.

**Blood pressure measurement by auscultation:** Procedure may cause temporary numbness/tingling in the arm. Blood pressure will be obtained by trained PCTRc nurses.

**Oral glucose tolerance test (OGTT) and at-home glucose challenge:** The risks associated with the OGTT are the same as those for having blood drawn as described above. The OGTT is safe and is used clinically in children and adults of all ages. Glucose is a normal nutrient found in many different foods. About one out in ten people have mild nausea or an upset stomach with the glucose (sugar) drink that is given during the OGTT. This can be minimized by drinking the sugar drink slowly over 5 minutes. Rarely, some people experience a mild low blood sugar reaction (symptoms like nervousness or sweating) at the end of the test. Participants will be offered a snack to guard against this from occurring.

**At-home mixed meal challenge:** Participants are at no greater risk than usual when they consume foods of choice at home. Examples of foods that would satisfy the requirement of 50g carbohydrate with fat and protein include: 1) 1 banana (27g carbs) and 2 slices of bread

---

with butter or peanut butter (30g carbs); 2) 1.5 cup Honey Bunches of Oats cereal (35g carbs) with 1 cup soy milk (15g carbs); 3) 8 oz strawberry yogurt (31g carbs) with 1 cup of fresh blueberries (21g carbs) or 1 medium apple (25g carbs).

**Wearing Dexcom G6 Pro device for 10 days:** The primary risks with Dexcom G6 Pro wear include skin irritation due to adhesive; bleeding, pain or infection at insertion site; and remote chance of sensor wire breakage. Skin irritation is common among children with type 1 diabetes (approximately 40-50%), but is significantly more common among individuals who have been using CGM (including removing and replacing) for more than 1 year (OR 0.3, versus less than 1 year) and is most frequently described as “eczema” (35%) or “dry wound” (8-14%).(Berg, Olsen et al. 2018) To minimize risk of irritation or poor adhesion, participants will be asked to refrain from using insect repellent, sunscreen, perfume, or lotion on their abdominal skin. To minimize risk of insertion complications, only trained study staff will place CGM on participants. Staff will clean and dry hands, then put on gloves before insertion. The insertion site will be cleaned with alcohol wipes, and device inserted after the skin is dry. The device will be placed away from waistbands, scarring, tattoos, irritation, or bones (such as hip bone). To minimize risk of sensor wire breakage upon removal, participants will be instructed on safe removal technique via a Dexcom-created video as well as explanation by study staff. Sterile broken or detached sensor wires pose minimal medical risk. Participants will be encouraged to call the study team with any concerns as soon as possible and informed that they may remove the device at any time if needed. If there is concern that the sensor wire has broken off under the skin, participants will be advised to not remove it, but to contact the study team. They may also contact Dexcom’s 24/7 Technical Support at [name]. Participants may require professional medical help if sensor wire is retained in skin, particularly if they have symptoms of infection or inflammation at the insertion site.

Participants will be asked to not undergo magnetic resonance imaging (MRI), computed tomography (CT), or diathermy while wearing CGM due to reading inaccuracies that may result from magnetic fields or heat.

**Wearing an ActiGraph GT9X physical activity and sleeper tracker on wrist:** Participants may experience discomfort or rash related to wearing the device. Participants will be allowed to remove the device at any time if needed due to discomfort or rash.

**Interview and disordered eating questionnaire:** Potential risks include momentary embarrassment or discomfort as well as breach of privacy and confidentiality. Participants may decline to answer any question during the interview for any reason. Every precaution will be taken to secure participants' personal information to ensure confidentiality.

**Sharing of private health information (PHI):** There is the potential risk for a breach of confidentiality. Private health information will be collected, accessed and stored according to HIPAA guidelines, including the use of multilevel password protection and enforcement of system user privileges on the database. To limit the risk of disclosure to the minimum necessary to conduct the study, all direct identifiers will be removed as soon as possible and codes will be substituted for personal identifiers. Records of individuals are stored with ID

---

numbers and a code with no discernible personal identifiers. Code lists and data files will be stored in separate, secure locations. Data will be stored on institutional secure servers hosted and accessed on password-protected computers. To maintain confidentiality, codes will be used in the database, presentations and publications.

